7.4. Randomization, Blinding and Unblinding

8. PATIENTS WHO MEET THE INCLUSION AND EXCLUSION CRITERIA WILL BE RANDOMLY ASSIGNED TO THE TREATMENT GROUP OR CONTROL GROUP, IN A 2:1 RATIO. PATIENTS IN THE TREATMENT GROUP WILL RECEIVE ACTIVE DIET SUPPLEMENTATION MEANWHILE, THE PATIENTS IN THE CONTROL GROUP WILL NOT RECEIVE ANY KIND OF MEDICATION OR PLACEBO. INVESTIGATIONAL PRODUCTS

The regular marketable merchandise of N-Pep-12 (Cebrium) capsules will be obtained from pharmaceutical wholesalers in Romania.

8.1. Name and Description of the Investigational Product(s)

N-Pep-12 (Cebrium)

For detailed information (Instructions for Use) on these products, please refer to Appendix 1.

8.1.1. Dosage, Formulations and administration

Active Diet Supplementation: N-Pep-12 (90 mg) capsules will be administered once per day.

8.2. Packaging and Labeling

Regular marketable merchandise will be used.

8.3. Storage

The study medication will be stored at room temperature in a dry place.

8.4. Investigational Product Accountability and Destruction

Not applicable.

9. CONCOMITANT THERAPY

There will be no restrictions on concomitant treatments or therapies for the study participants. However, any concomitant treatment or therapy will be recorded in the patient's CRF.

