Exclusion Criteria	Pre-existing and active major neurological disease	
	 Pre-existing and active (e.g., on chronic medication) major psychiatric disease, such as major depression, schizophrenia, bipolar disease, or dementia (the short Informant Questionnaire on Cognitive Decline in the Elderly (IQCODE) score >3) 	
	Advanced liver, kidney, cardiac, or pulmonary disease	
	A terminal medical diagnosis consistent with survival < 1 year	
	Major drug dependency, including alcohol (in the investigator's judgment).	
	 Injury of writing hand influencing cognitive or other outcome measures, in the investigator's judgment. 	
	Females who are pregnant or lactating.	
Visit Schedule	Visit 1 – Screening / Baseline	
	Day – Baseline - 30-120 days from stroke onset	
	Visit 2 – Efficacy / Safety	
	Day – 90 days from baseline	
	Visit 3 – Efficacy / Safety	
	Day – 360 days from baseline	
Documented parameters	Visit 1 – 30-120 days from stroke onset	
	Patient logistics	
	Patient demographic data (age, gender, ethnicity)	
	Patient medical history and risk factors	
	Patient medical history and risk factors	
	 Patient medical history and risk factors Inclusion/exclusion criteria 	

	QEEG/ET parameters	
	Visit 2 – 90 days from baseline	
	o Patient logistics	
	 All primary efficacy assessment scales 	
	o QEEG/ET parameters	
	Visit 3 – 360 days from baseline	
	o Patient logistics	
	 All primary efficacy assessment scales 	
	 QEEG/ET parameters 	
Statistical methods	The statistical analyses in this study will be exploratory in	
	nature because the study is not powered to address any	
	pre-defined statements but to generate valid hypotheses	
	on efficacy and safety issues for future studies. A formal	
	sample size calculation for confirmatory trials was not	
	performed.	

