3. INTRODUCTION

3.1. Background information

Cognitive impairment is a common finding in patients with stroke, regardless of severity, and it has an important impact on quality of life. Vascular cognitive impairment (VCI) describes a spectrum of cognitive disorders ranging from mild cognitive impairment (MCI) to dementia, with consequences for all cognitive domains and behavior (Jellinger K. A., 2013). However, there is increasing evidence to suggest the disproportionate impairment of executive function, including working memory, abstraction, reasoning, verbal fluency, and cognitive flexibility (Sachdev P.S. et al, 2004; Sörös P. et al., 2015). In epidemiological studies of stroke, cognitive impairment ranges from 20% to 80%; this variation depends on several factors, especially the diagnostic criteria (Sun J.H. et al., 2014). For example, the prevalence of the cognitive impairment 3 months after stroke can present a variation up to 72% depending on the complexity of the neuropsychological assessment (Gutiérrez P.C. et al., 2011; Douiri A., et al, 2013).

This is a pilot study to investigate the effects of N-Pep-12 diet supplementation on the neurorecovery of patients with post-stroke cognitive impairment. N-Pep-12 is a proprietary, peptide-based nutritional supplement that has been shown to exert neuroprotective and procognitive effects in experimental studies (Hutter-Paier B. et al., 2015) as well as in earlier

clinical studies in patients suffering from age-related cognitive deficits (Alvarez X.A. et al., 2005; Crook T.H. et al., 2005). Remarkably, N-Pep-12 has been shown to significantly improve memory impairment in older adults with subjective memory complaints after only 30 days of a once-daily intervention with 90 mg of the compound (Crook T. H. et al., 2005). The compound is available in the form of film-coated tablets or capsules under the brand names Memoprove and Cebrium. Furthermore, qEEG power analysis showed that N-Pep-12 is able to improve vigilance after only a single dose (Alvarez X.A. et al., 2005).

This study will use a multidimensional approach that will combine neuropsychological outcome scales, neurophysiological investigations (qEEG), psychophysiological investigations (eye-tracking), and clinical parameters.

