4. STUDY OBJECTIVES

The study shall assess the therapeutic effect and the safety of a single daily dose of 90 mg of N-Pep-12 in supporting neurorecovery in comparison to a control group of patients after stroke. This is an exploratory study, and the dosage, route of administration and intervention duration were chosen according the current instructions for use provided by the manufacturer of N-Pep-12. The study aims to show the superiority of N-Pep-12 over the control group in the neurorecovery outcome after 360 days.

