12. STUDY SCHEDULE

12.1. Procedures at Each Visit

Visit 1: Screening/Baseline - 30-120 days from stroke onset

Patients will be informed about the study and an Informed consent will be obtained before any study-specific procedures will be carried out. Inclusion/exclusion criteria will be assessed and documented in the CRF. Patients who provide an informed consent and who meet all inclusion/exclusion criteria will be included in the study, and a randomization code will be assigned. After randomization, the medical history, vital signs, and patient demographic data as well as any concomitant medication will be measured or retrieved and recorded in the CRF. The baseline tests for all efficacy parameters (primary and secondary) will then be administered, and the results will be recorded in the CRF. Treatment with the study drug will be initiated with the first dose, and patients will receive the study drug for first 90 days of treatment.

Visit 2: 90 days from baseline

Vital signs will be taken, and changes in any of the concomitant medications will be recorded in the CRF. Any adverse events reported by the patient or noted by the investigator will be assessed and recorded in the CRF. Compliance with the study medication will be checked and recorded in the CRF. Tests for primary and secondary efficacy parameters will be administered and recorded. Patients will receive the study drug for the next 270 days of treatment.

VISIT 3: 360 days from baseline

Vital signs will be taken, and changes in any of the concomitant medications will be recorded in the CRF. Any adverse events reported by the patient or noted by the investigator will be assessed and recorded in the CRF. Compliance with the study medication will be checked and recorded in the CRF. Tests for primary and secondary efficacy parameters will be administered and recorded.

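### Section 9 leaves concomitant treatment unrestricted without excepting N-Pep-12, and 7.2 does not exclude current users, so controls may take the marketed product and dilute the day-360 difference

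*Protocol*

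**What the plan says.** Section 4 of the protocol sets the contrast: "The study aims to show the superiority of N-Pep-12 over the control group in the neurorecovery outcome after 360 days". Section 5 makes the study open label. Section 7.4 allocates patients 2:1 and says that "THE PATIENTS IN THE CONTROL GROUP WILL NOT RECEIVE ANY KIND OF MEDICATION OR PLACEBO". The synopsis plans 60 patients on N-Pep-12 and 30 in the reference group.

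The product is on sale. Section 3.1 says "The compound is available in the form of film-coated tablets or capsules under the brand names Memoprove and Cebrium", and Section 8 says "The regular marketable merchandise of N-Pep-12 (Cebrium) capsules will be obtained from pharmaceutical wholesalers in Romania". The single site is in Cluj-Napoca, Romania.

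On other treatment, Section 9 says "There will be no restrictions on concomitant treatments or therapies for the study participants", and adds only that "any concomitant treatment or therapy will be recorded" in the CRF. N-Pep-12 is not excepted. Section 7.2 lists seven exclusions: neurological disease, psychiatric disease, organ disease, terminal illness, drug dependency, injury of the writing hand, and pregnancy or lactation. None concerns use of N-Pep-12, and Section 7.1 adds no such condition.

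The synopsis describes the analyses as exploratory in "nature because the study is not powered to address any" pre-specified claim, and no formal sample size calculation was made.

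**The concern.** The comparison is informative only to the extent that controls are not exposed to N-Pep-12. Controls know that they are not getting it, the follow-up lasts almost a year, and the product can be bought. No rule in the visible protocol stops a control from taking it or keeps out a patient who already does.

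At stake is an understated effect estimate. The direction is conservative, so this does not raise the risk of a false claim of superiority. For a study meant to generate hypotheses for later trials, the harm is that a real effect looks smaller than it is. Once contamination has happened it cannot be undone at the analysis stage without leaving the plain randomised comparison.

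**Working it through.** **The text.** Three provisions could close the gap.

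| Provision | What it does | Does it keep controls unexposed? |
|---|---|---|
| 7.4, control condition | States what each arm is given | Shows the intent. It cannot be a literal ban on all medication for stroke patients, since Section 9 allows any treatment. It does not forbid self-purchase |
| 7.2, exclusions | Seven criteria | No criterion on current use |
| 9 and 12.1, CRF recording | Documents concomitant treatment | Detects use but does not prevent it |

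On timing, Section 12.1 says "Inclusion/exclusion criteria will be assessed and documented in the CRF" and then has the randomisation code assigned. Concomitant medication is retrieved and recorded only after that. The planned record therefore cannot serve as a screen for current users.

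**The size.** The protocol states no power, effect size, SD or uptake rate, so there is no figure to reproduce. Everything below except the group sizes is an assumption.

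Inputs: 60 and 30 patients (synopsis); c = share of controls exposed; f = share of the full effect that they get; δ = true effect in SD units.

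The treated mean is shifted by δ and the control mean by c·f·δ, so

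expected difference = δ − c·f·δ = (1 − c·f)·δ.

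| Uptake c | Effect lost, f = 1 | Effect lost, f = 0.5 |
|---|---|---|
| 0 | 0% | 0% |
| 1 of 30 | 3.3% | 1.7% |
| 5% | 5% | 2.5% |
| 10% | 10% | 5% |
| 20% | 20% | 10% |

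To set this against the precision of the study:

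- Standard error of the difference = √(1/60 + 1/30) = √0.05 = 0.2236 SD.
- 95% half-width (t, 88 df) = 0.444 SD.

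| Assumed δ | Loss at c = 1/30, f = 1 | Loss at c = 10%, f = 1 |
|---|---|---|
| 0.3 SD | 0.010 SD = 0.045 SE | 0.030 SD = 0.13 SE |
| 0.5 SD | 0.017 SD = 0.075 SE | 0.050 SD = 0.22 SE |
| 0.8 SD | 0.027 SD = 0.119 SE | 0.080 SD = 0.36 SE |

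For scale only, since the study claims no power: with a two-sided 5% test and δ = 0.5 SD, 60 against 30 patients give 60.9% power with no contamination, 52.1% at 10% uptake and 43.2% at 20%, both at full effect.

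**The case against.** The strongest reply is that Section 9 concerns background care. N-Pep-12 is the investigational product, and concomitant treatment normally means what is taken alongside the assigned regimen. Section 7.4 fixes the control condition, so a general sentence on other therapies should not be read as overriding it. That is a fair account of what was intended. It does not supply a rule: 7.4 describes what the study gives, and Section 9 as worded allows everything else.

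Second, an instruction to controls may sit in the consent form. The text of Appendices 1 and 2 was not available for this review, so the point is limited to the visible protocol. Eligibility and permitted treatments nevertheless belong in the body of the protocol.

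Third, Section 12.1 orders the recording and does not say that medication is unknown at eligibility. The psychiatric exclusion already calls for some knowledge of chronic medication. That is right, and the order of recording is not a separate defect: with no current-use criterion there is nothing to screen for. It matters only in showing that the existing record does not fill the gap.

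Fourth, nothing in the documents shows that controls would seek the product. Use is recorded, the study is exploratory, and leaving background care free is a legitimate Phase IV choice. All of this stands and limits the weight of the point. CRF data would support a supplementary analysis that accounts for reported users, but that would no longer be the plain randomised comparison. Free background care does not require leaving the test product itself unrestricted.

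**Conclusion.** The concern holds. The visible protocol states a rule of no restrictions, makes no exception for the test product and has no exclusion for current users, while the comparison depends on unexposed controls.

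The bias is towards zero and its size is unknown. Under the assumption that exposed controls get the full effect, the loss equals the share exposed: 3.3% for one control in 30, 10% at 10% uptake and 20% at 20%; it is half that at half effect, and nil if nobody takes the product. At 10% uptake and full effect it amounts to 0.13 to 0.36 of a standard error for true effects of 0.3 to 0.8 SD. That is small against the study's own imprecision. This is a cheap improvement to the protocol, not a flaw that undermines it.

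**What to change.** 1. Add an exclusion to Section 7.2 and the synopsis: *Current use of N-Pep-12 (Memoprove or Cebrium).* Ask about it by brand name in the Visit 1 eligibility check, before randomisation.
2. Add an exception to Section 9, for example: *Other treatment is unrestricted, but N-Pep-12 (Memoprove or Cebrium) outside the study allocation is not permitted in either arm through day 360. Any such use is recorded in the CRF as a protocol deviation, and the patient remains in the as-randomised comparison.* When concomitant medication is reviewed at Visits 2 and 3, ask about N-Pep-12 by name.

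The cost is one exclusion line, one exception, a short question at each visit, and the loss of the few screened patients who already take the product. All other care stays unrestricted. The change reduces dilution but cannot guarantee its absence, because a written ban will not bring uptake of a purchasable product to zero.

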10. DEFINITION OF THE PRIMARY AND SECONDARY VARIABLES

Five neuro-psychological scales will be used in stroke patients: MoCA, HADS, CTT, DS and PSI. These scales have been established as reliable and valid and have been used extensively in other clinical trials on stroke and cognitive impairment (Quinn T.J., 2011; Aben I., 2002; Pendlebury S. T., 2013; Poon W., 2015).

10.1. Primary Variables

MoCA

Montreal Cognitive Assessment (MoCA) was designed as a rapid screening instrument for mild cognitive dysfunction. It assesses different cognitive domains: attention and concentration, executive functions, memory, language, visuo-constructional skills, conceptual thinking, calculations, and orientation. The time to administer the MoCA is approximately 10 minutes. The total possible score is 30 points; a score of 26 or above is considered normal.

• Processing Speed Index, Wechsler Adult Intelligence Scale, Fourth Edition

The Processing Speed Index (PSI) assesses skills such as focusing attention and quick scanning as well as discriminating between and sequentially ordering visual information. It requires persistence and planning ability, but it is sensitive to motivation, difficulty working under time pressure, and motor coordination as well. It is also related to reading, mathematical, and memory skills. Cultural factors seem to have little impact on processing speed. Processing Speed (PS) refers to the speed at which cognitive processes can be performed.

• Digit Span, Wechsler Adult Intelligence Scale, Fourth Edition

The Digit Span task exercises a patient's verbal working memory. Attention and comprehension also contribute to performance. The digit span task is a common component of many IQ tests, including the widely used WAIS (Wechsler Adult Intelligence Scales).

Performance on the digit span task is also closely linked to language learning abilities. The procedures for this assessment of working memory are considered standard. A list of numbers is read out loud at a rate of one number per second, and the participant is then asked to recall the numbers in order. The first list consists of three numbers and increases until the person begins to make errors. Lists with recognizable patterns (e.g., 1, 3, 5, 7, and 9) should be avoided, as people may remember these numbers more easily. At the end of each sequence, the participant is asked to the recall items in order. The average adult can remember a sequence of seven numbers, plus or minus two. This test can be distributed both backwards and forwards. Scores are thought to correlate with age and not intelligence.

Hospital Anxiety and Depression Scale

The Hospital Anxiety and Depression Scale (HADS) is commonly used to determine a patient's levels of anxiety and depression. The HADS is a fourteen item scale that generates: seven of the items relate to anxiety and seven relate to depression. Each item had been answered by the patient on a four-point (0–3) response category so the possible scores ranged from 0 to 21 for anxiety and 0 to 21 for depression. A score of 0 to 7 could be regarded as being in the normal range, a score of 8 to 10 as borderline abnormal, and a score over 11 as abnormal. The patient is asked to provide answers regarding his/her feelings during the past week. While answering the questions, the patient should answer with immediate reactions, thus giving a more accurate representation of his/her feelings.

Color Trails Test

The Color Trails Test (CTT) was developed to meet the need for a test with the sensitivity and specificity of the standard Trail Making Test (TMT) but that was as free as possible from the influences of language and cultural bias. The CTT retains the psychometric properties of the standard TMT, but the CTT substitutes the use of color for the use of English alphabet letters, making it more suitable in cross-cultural and other special needs contexts.

10.2. Secondary variables

- AE, SAE
 - Date/time
 - Relationship/Seriousness/Outcome
- Mortality:
 - o Date/time
 - Cause

Combined Neuropsychological, Neurophysiological and Psychophysiological Assessment of the Effects of N-Pep-12 on Neurorecovery in Patients after Ischemic Stroke

- Subgroup analysis
 - QEEG parameters
 - Eye tracking parameters

10.3. Source Documents

Variable	Source document
Informed consent	Informed consent form
Patient's data (e.g., demographics: sex, age, weight, indication, concomitant diseases, medical history, concomitant medication)	
Vital signs	CRF
Outcome variables (evaluation scales)	CRF
Patient safety data	CRF

11. ASSESSING AND REPORTING OF ADVERSE EVENTS

Throughout the course of the clinical study, particular attention will be paid to the adverse events and adverse drug reactions mentioned below.

11.1. Adverse Events (AE)

An adverse event (AE) is any untoward medical occurrence in a patient or subject of clinical investigation administered a pharmaceutical product and that does not necessarily have a causal relationship with this treatment. An AE can therefore be any unfavorable and unintended sign (including an abnormal laboratory finding), symptom, or disease temporally associated with the use of an investigational product, whether or not it is related.

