2. PROTOCOL SUMMARY / SYNOPSIS

Title	Combined Neuropsychological, Neurophysiological and	
TIGG		
	Psychophysiological Assessment of the Effects of N-Pep-	
	12 on Neurorecovery in Patients After Ischemic Stroke –	
	N-PEP-12 EXTENSION	
Name of product	MemoProve / Cebrium	
Name of active substance	N-PEP-12	
Phase	Phase IV	
Indication	Ischemic Stroke	
Study Design	Exploratory, prospective, randomized, open label, controlled study	
Number of sites & countries	1 center Romania	
Sample Size	Stroke Group – minimum 90 patients	
	Intervention Group: N = 60	
	Reference Group: N = 30	
Primary Objectives	To assess the efficacy of 360 days of once-daily diet supplementation with 90 mg N-Pep-12 on the neurocognitive function and neurorecovery outcome in patients with post-stroke cognitive impairment.	
Secondary Objectives	 To assess the safety of 360 days of once-daily diet supplementation with 90 mg N-Pep-12 on the neurocognitive function and neurorecovery outcome in patients with post-stroke cognitive impairment. To assess study group baseline differences between N-PEP-12 treated patients and controls using quantitative electroencephalography (QEEG) and eye tracking (ET) at day 360, in patients with available recordings (subgroup 	

Combined Neuropsychological, Neurophysiological and Psychophysiological Assessment of the Effects of N-Pep-12 on Neurorecovery in Patients after Ischemic Stroke

	analysis).	
Primary Variable	Stroke Group	
	Montreal Cognitive Assessment (MoCA)	
	 Hospital Anxiety and Depression Scale (HADS) 	
	Digit Span (DS)	
	Color Trial Test (CTT)	
	Processing Speed Index (PSI)	
Secondary Variables	AE, SAE Date/time	
	Deletionalia (Oesianos es /Oesta	
	o Relationship/Seriousness/Outco	
	Mortality:	
	Date/time	
	o Cause	
	Subgroup analysis	
	 QEEG parameters 	
	 Eye tracking parameters 	
Inclusion Criteria	Stroke onset – 30-120 days prior to screening	
	Stroke is ischemic in origin, supratentorial, and radiologically confirmed (CT or MRI)	
	No significant pre-stroke disability (pre-stroke Modified Rankin Score of 0 or 1)	
	Goodglass and Kaplan Communication Scale	
	Score of > 2 at screening	
	No other radiologically confirmed stroke in the	
	3 months preceding index stroke	
	Age between 18 and 80 years, inclusive	
	Signed informed consent form	

Combined Neuropsychological, Neurophysiological and Psychophysiological Assessment of the Effects of N-Pep-12 on Neurorecovery in Patients after Ischemic Stroke

Fuelveien Oritorie		

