7.3. Stopping and Discontinuation Criteria

7.3.1. Discontinuation Criteria related to the Study

- Insufficient recruitment of less than 30% of the total patient sample in one year
- If reasonable suspicion exists that any serious and life-threatening side effects occur significantly more frequently than usual in patients with the inclusion diagnosis, the study will be discontinued.

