11.3. Serious Adverse Event or Serious Adverse Reaction (SAE/SAR)

An adverse drug reaction is considered SERIOUS if it:

- Results in death
- Is life threatening

- Requires additional inpatient hospitalization or prolongation of existing hospitalization
- Results in persistent or significant disability / incapacity
- Results in a congenital anomaly or birth defect
- Other medically significant event that requires immediate medical or surgical intervention

An adverse drug reaction is considered UNEXPECTED if it:

Is not consistent with the Investigators' Brochure or SPC

CAUSAL RELATIONSHIP means:

- There are facts/evidence to suggest a causal relationship
- As judged by the reporting health care professional to have a reasonably suspected causal relationship

Expedited Reporting is required if all of the following criteria apply (ICH E2A):

- Serious
- Unexpected
- Causal relationship to study treatment

NOTE

Death: is the outcome of an adverse event. The event to be reported comprehensively is the medical condition leading to death, e.g., underlying disease or accident.

Life-threatening: in the definition of a serious adverse event or adverse reaction, "life-threatening" refers to an event in which the patient was at risk of death at the time of the event; it does not refer to an event that hypothetically might have caused death if it was more severe.

Medical judgment should be exercised in deciding whether an adverse event/reaction is serious in other situations. Important adverse events/reactions that are not immediately life-threatening or do not result in death or hospitalization but may jeopardize the patient or may require intervention to prevent one of the other outcomes listed in the definition above should also be considered serious.

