11.6. Recording of Adverse Events

All adverse events, whether they are considered serious or not, will be documented and applicably reported according to previously provided definitions.

The investigator must report in detail all adverse signs and symptoms that are either volunteered by patients or observed during or following the course of Investigational Product administration on the appropriate CRF page.

Included in the description should be the nature of the sign or symptom; the date of onset; date of resolution (duration); the severity/intensity; the relationship to the study treatment or other therapy; the action taken (if any); and the outcome.

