11.7. Reporting of Serious Adverse Events

All serious adverse reactions and all unexpected serious adverse reactions with at least a suspicion of a causal relationship to the investigational product must be reported to the manufacturer within 24 hours (one working day) of the Investigator first becoming aware.

Fatal or life-threatening SUSARs must be reported to the Ethics Committee and relevant regulatory bodies within 7 days; all other SUSARs must be reported within 15 days of knowledge if no other timelines are set out in the local drug law.

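### Adverse-event and seriousness wording is built around product exposure, so the plan does not ensure comparable AE/SAE recording in the untreated control arm

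*Protocol*

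**What the plan says.** Section 4 sets out to assess both therapeutic effect and safety against a control group. Section 4.2 makes safety the secondary objective, and section 10.2 lists AEs, SAEs and mortality as secondary variables. The study is open label (section 5). Under section 7.4 patients are "RANDOMLY ASSIGNED TO THE TREATMENT GROUP OR CONTROL GROUP, IN A 2:1 RATIO", and "THE PATIENTS IN THE CONTROL GROUP WILL NOT RECEIVE ANY KIND OF MEDICATION OR PLACEBO". The synopsis gives "Intervention Group: N = 60", with 30 in the reference group.

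Some passages tie adverse events to exposure or to a drug reaction:

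- Section 11.1 defines an AE as "any untoward medical occurrence in a patient or subject of clinical investigation administered a pharmaceutical product". Its second sentence requires a temporal link to use of an investigational product, regardless of causality.
- Section 11.3 opens its list of criteria with "An adverse drug reaction is considered SERIOUS if it". Section 11.2 defines such a reaction as a response to the investigational product that the investigator judges causal.
- Section 11.6 requires detailed reporting of signs and symptoms volunteered by patients or "observed during or following the course of Investigational Product administration on the appropriate CRF page".
- Section 11.7 is headed as covering serious adverse events, but its text covers "All serious adverse reactions and all unexpected serious adverse reactions with at least a suspicion of a causal relationship".

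Other passages are not limited in this way. The heading of 11.3 names both events and reactions, and its notes speak of both. The first sentence of 11.6 has every AE documented, serious or not. Section 12.1 has any AE recorded at Visits 2 and 3, and the table in 12.2 lists adverse events at all three visits, in each case with no limit by arm.

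Separately, section 7.3.1 provides for stopping the study if serious and life-threatening side effects are reasonably suspected to "occur significantly more frequently than usual in patients with the inclusion diagnosis".

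**The concern.** A safety comparison between randomised arms needs one event definition, one observation window and one recording duty for both arms. Here the definitions are worded for patients who take the product, and one arm does not. Site staff know each patient's arm. Someone who applies section 11 literally could conclude that an untoward occurrence in a control patient is not an AE, or that a hospitalisation in a control patient does not meet the lead-in to the seriousness list. Someone who follows section 12 would record both.

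At stake is whether the AE and SAE counts in the two arms measure the same thing. If control events are recorded less completely, the product looks less safe than it is. The study is exploratory, but the synopsis gives the generation of valid safety hypotheses for later studies as one of its purposes, and unequal recording would undermine that.

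**Working it through.** **Comparison of the passages.** The protocol gives no event rate, safety test or capture rate, so there is no stated figure to reproduce. The main check is textual.

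1. *Can a control patient have an AE under 11.1?* The first sentence asks for administration of a pharmaceutical product. Section 9 leaves concomitant treatment unrestricted, so a control patient on other drugs could satisfy it. The second sentence asks for use of an investigational product, which a control patient cannot satisfy. Sections 12.1 and 12.2 nevertheless have AEs recorded with no limit by arm.
2. *Can a control patient have an SAE under 11.3?* The lead-in requires an adverse drug reaction, and by 11.2 an untreated patient has none. The heading and notes apply seriousness to events as well. The section is inconsistent within itself.
3. *Over what period is a control patient's event recorded under 11.6?* The first sentence covers all AEs but refers back to the definitions already given, which leads to 11.1. The next sentence uses a window set by product administration, and controls have no such window.

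**Illustration on assumed inputs.** This shows how unequal capture would act. It does not estimate what will happen here.

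- From the synopsis: 60 treated and 30 controls (60 + 30 = 90; 60/30 = 2:1).
- Assumed: the same true risk *p* of at least one AE in both arms; complete recording in the treated arm; a share *c* of affected control patients recorded; Fisher's exact test at two-sided 0.05.
- Expected patients with a recorded AE: 60*p* treated and 30*pc* control.
- Spurious risk difference: *p* − *pc* = *p*(1 − *c*). For example, 0.30 × (1 − 0.5) = 0.15.
- Chance of a false significant difference: sum over all pairs of binomial outcomes for which the test rejects.

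| *p* | *c* | Expected, treated | Expected, control | Spurious difference (points) | Chance of false significance |
|---|---|---|---|---|---|
| 10% | 1 | 6 | 3 | 0 | 3.1% |
| 10% | 0.8 | 6 | 2.4 | 2 | 3.1% |
| 10% | 0.5 | 6 | 1.5 | 5 | 5.7% |
| 20% | 1 | 12 | 6 | 0 | 3.6% |
| 20% | 0.8 | 12 | 4.8 | 4 | 4.9% |
| 20% | 0.5 | 12 | 3 | 10 | 15.9% |
| 30% | 1 | 18 | 9 | 0 | 3.7% |
| 30% | 0.8 | 18 | 7.2 | 6 | 7.0% |
| 30% | 0.5 | 18 | 4.5 | 15 | 30.8% |
| 50% | 1 | 30 | 15 | 0 | 4.4% |
| 50% | 0.8 | 30 | 12 | 10 | 13.0% |
| 50% | 0.5 | 30 | 7.5 | 25 | 60.3% |

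With equal capture (*c* = 1) the spurious difference is zero. Recording no control events at all (*c* = 0) would give a 30-point difference at *p* = 30%, but the visit procedures in 12.1 and 12.2 make that case unlikely.

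**The case against.** The strongest reply is that the protocol, read as a whole, already records events in everyone. AEs are collected at the visits with no limit by arm, and section 10.2 lists AE, SAE and mortality without such a limit. Mortality, with date and cause, is a variable of its own, so control deaths would be counted however an AE is defined. In 11.6 the product-administration window may qualify only what is observed, not what patients volunteer. On this view one lead-in line and a standard definition are loosely worded, in an exploratory study with no powered claims.

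Much of this stands, and it rules out several stronger readings that a reader might infer:

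- *That seriousness is defined only for drug reactions.* The heading and notes of 11.3 extend it to events.
- *That serious events judged unrelated are lost.* Section 11.1 includes unrelated events, 11.6 has all AEs documented with their relationship to treatment, and the causality scale in 11.6.2 has categories for unlikely and unrelated events.
- *That 11.7 removes control events from the data.* It governs reports to the manufacturer, the ethics committee and regulators, not what enters the CRF.
- *That the criterion in 7.3.1 cannot draw on the control arm.* Controls are patients with the inclusion diagnosis, and nothing forbids using them.

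The reply does not remove the conflict. Section 11.6 ties documentation to the earlier definitions, and the second sentence of 11.1 cannot be met by a patient who takes no investigational product. A site must choose which text to follow, knowing the patient's arm.

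**Conclusion.** The point holds as an inconsistency that leaves comparable recording unsecured. Sections 11.1, 11.3 (lead-in) and 11.6 (detailed duty) are worded around product exposure or drug reactions. Sections 12.1 and 12.2 record events in all patients. The stated safety comparison is with an arm that takes no product.

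It would go too far to say that the two arms cannot yield comparable counts, or that the safety comparison is biased. The visit procedures make some, and perhaps full, control capture likely, and the protocol gives nothing from which capture could be estimated. What can be said is that there is a risk of under-recording in controls, whose direction would be against the product. The percentages in the table depend wholly on the assumed risk, capture share and test.

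Two lesser mismatches belong with this. The heading of 11.7 promises serious adverse events while its text covers reactions only. In 7.3.1 the comparison with what is usual names no reference, although a concurrent control arm exists.

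**What to change.** - **11.1:** define an AE as an untoward medical occurrence in any randomised patient from randomisation to the day-360 visit, whether or not product was taken.
- **11.3:** introduce the seriousness list for any adverse event, so that the lead-in agrees with the heading and notes. Reactions then follow as the subset judged causal.
- **11.6:** replace the product-administration window with the same randomisation-to-day-360 window, and state that recording is identical in both arms, in line with 12.1 and 12.2.
- **11.7:** reconcile the heading with the text, so that it is clear which serious events the section covers.
- **7.3.1:** the sponsor should state what reference the comparison has in mind and reconcile it with the presence of a concurrent control arm. No stopping rule is proposed here.

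The cost is a few sentences and slightly more event recording in controls, with no new visit. The change is best made before data collection, since control events that were not recorded may not be recoverable later.
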